10.1.6 Endpoint

Neurophysiological changes from baseline in qEEG, peak amplitudes (and latencies) of MMN, auditory and visual target P3b and novelty P3a, auditory N1 and visual P1, ASSR total power and ITC (inter-trial phase coherence) for 20, 30, and 40 Hz driving conditions, and baseline gamma power assessed during the ASSR paradigm, will be investigated and their differences between groups will also be investigated.

10.1.8 Statistical Considerations

10.1.8.1 Statistical Design – Model

An exploratory analysis will be conducted on EEG signals across electrodes and temporal windows to examine drug effects on EEG variables.

10.1.8.2 Null and Alternative Hypotheses

It is not planned to test any statistical hypotheses with regard to any of the endpoints of this EEG sub-study in a confirmatory sense. For the evaluation, a two-sided 95% confidence interval (CI) of adjusted treatment differences will be computed. However, the CI will have to be interpreted in the perspective of the exploratory character of the sub-study, i.e. as an interval estimate for effects under these conditions.

10.1.8.3 Planned Analyses

The statistical model used for the analysis of the EEG endpoints will be an ANOVA (analysis of variance) model. This model will include effects for treatment, age and possibly other effects that will be specified in detail in the TSAP. Further descriptive statistics, including boxplots, will be provided. The variables may be transformed onto a logarithmic scale if severe skewedness is present. More details will be described in the TSAP.

Correlational analyses with clinical endpoints may be made and details therefore will be described in the TSAP.

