4. TREATMENTS

4.1 INVESTIGATIONAL TREATMENTS

BI 409306, as a film-coated tablet, will be produced by Boehringer Ingelheim Pharma GmbH & Co. KG.

Each film-coated tablet contains 50 mg BI 409306.

Eligible patients are randomly assigned to double blind treatment at a ratio of 1:1 of placebo or 50 mg b.i.d. BI 409306 (c.f. [Section 4.1.4](#) and [Table 4.1.4:1](#)).

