7.7 DETERMINATION OF SAMPLE SIZE

Remission rate of the population diagnosed with APS and without intervention was assumed to be 40% ([R16-0991](#)) by 52 weeks. The rate of remission for BI 409306 was assumed to be 57% by 52 weeks. This will lead to a hazard ratio of 1.652.

Other study considerations are:

- Two-sided alpha = 0.10
- Dropout = 20% after one year
- Interim analysis checking for early efficacy using user-defined alpha-spending boundary of 0.01 at the 67% information point

Table 7.7: 1 Power calculations for sample size (for both arms combined) of 300 for various remission rates for BI 409306 with fixed placebo group aggregate first remission rate prediction of 40% by 52 weeks

Remission Rate for Placebo	Remission Rate for BI 409306	Hazard Ratio	Risk Ratio	Power for N=300	# Events needed in total
40%	52%	1.437	1.300	64.9%	126
40%	55%	1.563	1.375	81.5%	130
40%	57%	1.652	1.425	89.3%	133
40%	59%	1.745	1.475	94.4%	136
40%	61%	1.843	1.525	97.4%	139

[Table 7.7: 1](#) displays the power achieved for 300 total randomized patients given a group aggregate first remission rate of 40% for placebo with two-sided $\alpha = 0.10$ and a user-defined

alpha spending boundary at interim analysis of $\alpha=0.01$ (two-sided). Group remission rates for BI 409306 treatment of 52%, 55%, 57%, 59% and 61% are considered. Total number of events needed to achieve the power reported is also shown.

Given remission rates of 40% for patients treated with placebo and 57% for patients treated with BI 409306, the risk ratio is 1.425 (implying that patients treated with BI 409306 will have 42.5% more chance of achieving remission of APS compared to placebo). A sample size of 300 (or 150 per group) was selected as the most logical for establishing proof of concept based on the risk / benefit considerations noted above. In addition this was the sample size used in the previous protocol and is kept the same. This translates to 89% power. The type I error was selected to be 10% since this is a phase II study meant to provide an understanding of the effectiveness of the drug without being too strict as in a confirmatory setting.

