10.1.3 Selection of Study Population

This sub-study will enroll up to 80 patients from a subset of sites participating in the 1289-0032 study, for exploratory purposes.

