10.1.4 Sub-study Design

Resting state EEG, auditory and visual ERP measures, baseline EEG gamma power and 40 Hz ASSR power and phase synchrony measures, will be explored and evaluated at the baseline Visit 2 (pre-dose) and EOT from a subset of the main study patient population.

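### Protocol 10.1.8.3 does not name the pre-dose EEG value as a covariate for the change-from-baseline EEG endpoints; naming it would narrow the intervals by about 2% to 13% at no data cost.

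*Protocol*

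**What the plan says.** Protocol 10.1.6 defines the EEG endpoints as changes: "Neurophysiological changes from baseline in qEEG, peak amplitudes (and latencies) of MMN", followed by the P3, N1, P1, steady-state-response and gamma-power measures. Under 10.1.4 these measures "will be explored and evaluated at the baseline Visit 2 (pre-dose) and EOT", so every patient with a change score also has a pre-dose value.

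On the analysis, 10.1.8.3 states: "The statistical model used for the analysis of the EEG endpoints will be an ANOVA (analysis of variance) model". It continues: "This model will include effects for treatment, age and possibly other effects that will be specified in detail in the TSAP". It then defers further detail to the SAP. No confirmatory test is planned; under 10.1.8.2, "a two-sided 95% confidence interval (CI) of adjusted treatment differences will be computed", to be read as exploratory. On size, 10.1.3 states: "This sub-study will enroll up to 80 patients from a subset of sites participating in the 1289-0032 study, for exploratory purposes".

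For comparison, the main-trial model for change-from-baseline endpoints (Protocol 7.3.2, repeated in SAP 7.5.2) includes the baseline score, its interaction with visit, and baseline antipsychotic use.

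The readable SAP has no EEG model, and its abbreviation list has no entry for EEG, ERP or MMN. However, its table of contents shows blacked-out entries after 5.2.2 and after 7.5.2, where further endpoints and their analyses would be expected.

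**The concern.** A change score adjusted only for treatment and age subtracts the baseline with a fixed coefficient of one. If the correlation between the two recordings is below one, that over-corrects. A patient with a high baseline tends to fall and one with a low baseline tends to rise, so a chance difference in baseline between arms passes partly into the estimated treatment difference. Entering the baseline value as a covariate lets the data set the coefficient and removes that component.

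The sub-study is small, and randomisation is stratified by antipsychotic use, not by sub-study membership. The interval for the adjusted difference is its only planned inference on treatment, so the covariate list bears directly on that result. The two parts of the protocol also treat the same kind of endpoint differently without giving a reason.

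**Working it through.** The documents give no SD, power or precision target for the EEG sub-study, so there is no stated figure to reproduce. The check compares the two models.

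**Inputs**
- Sample size: 80, the maximum in Protocol 10.1.3.
- Split: 40:40. This is an assumption. Protocol 4.1 says "Eligible patients are randomly assigned to double blind treatment at a ratio of 1:1", but that applies to the whole trial.
- Evaluable patients: Protocol 7.7 gives "Dropout = 20% after one year" for the main trial. Applied here as an assumption, 80 × 0.8 = 64.
- Correlation r between baseline and week 52: the only figure is an intraclass correlation of about 0.90 for mismatch negativity in chronic patients over one to two years (Protocol 10.1.2.1). None is given for P3, steady-state or resting measures, nor for this population. I use 0.9 and assume 0.7 and 0.5 as lower values.
- Equal SD at both visits (set to 1), a linear relation, and age unrelated to the EEG measure.

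**Residual variance**
- Change score without baseline: 2(1 − r)
- With baseline as covariate: 1 − r²
- Ratio, with to without: (1 − r²) / [2(1 − r)] = (1 + r)/2

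This gives 0.95 at r = 0.9, 0.85 at r = 0.7 and 0.75 at r = 0.5.

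**Where the excess comes from**

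2(1 − r) = (1 − r²) + (1 − r)². The second term is the baseline difference carried into the change score:
- r = 0.9: 0.20 = 0.19 + 0.01
- r = 0.7: 0.60 = 0.51 + 0.09
- r = 0.5: 1.00 = 0.75 + 0.25

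With 40 per arm, one standard error of baseline imbalance is √(2/40) = 0.22 SD. The change score carries (1 − r) times that: 0.02, 0.07 and 0.11 SD respectively. This is the same loss as the larger variance, seen conditionally on the observed imbalance; it is not a second loss.

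**Width of the 95% interval**

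Half-width = t × √(residual variance × 2/n per arm × allowance for estimating the covariates). Without baseline there are N − 3 degrees of freedom and the allowance is 1 + 1/(N − 4). With baseline there are N − 4 and it is 1 + 2/(N − 5).

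Worked case, N = 80 and r = 0.5:
- Without: 1.991 × √(1.00 × 0.05 × 1.0132) = 0.448
- With: 1.992 × √(0.75 × 0.05 × 1.0267) = 0.391
- Reduction: 1 − 0.391/0.448, about 12.8%

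| r | Half-width without (SD units), N = 80 | With, N = 80 | Narrower, N = 80 | Patients needed without baseline for equal width | Narrower, N = 64 |
|---|---|---|---|---|---|
| 0.9 | 0.200 | 0.197 | 1.9% | about 83 | 1.7% |
| 0.7 | 0.347 | 0.322 | 7.2% | about 93 | 7.0% |
| 0.5 | 0.448 | 0.391 | 12.8% | about 105 | 12.6% |

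A simulation of 1,500 runs per case gave reductions at N = 80 of 1.9%, 7.5% and 12.8%.

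**The case against.** The strongest reply is that the model in 10.1.8.3 is not closed. The sentence on model terms allows further effects, the section defers detail to the SAP, and 10.1.8.2 speaks of adjusted differences. The SAP parts where an EEG analysis would sit cannot be read, and blacked-out text is not missing from the plan. This stands. A reader might infer that the trial decided to leave baseline out, or that the final analysis did so. The documents support neither. The absence of EEG terms from the SAP abbreviation list is weak evidence and does not show which model was used. What remains is that the protocol's wording commits to nothing beyond treatment and age.

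The second reply is that the gain is very small at the one documented correlation. That also stands for mismatch negativity if the figure carries over. It may not: it comes from chronic patients, and 10.1.2.1 itself says that these deficits can improve as patients become more stable and that P3b shows some sensitivity to clinical state. Lower correlations for some measures are plausible, but no figure supports a particular value.

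A third reply concerns bias. A reader might infer that the unadjusted comparison is biased. Under randomisation it is not; chance imbalance is part of its sampling variance.

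Finally, the sub-study is exploratory, with no test and no precision target. That limits the importance of the point but gives no reason to leave out a value already recorded.

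**Conclusion.** The point holds as a low-cost improvement to the specification. The protocol names treatment and age, does not name the baseline value, and differs in this from its own main-trial model; no readable SAP text fills the gap. It cannot be said that precision was actually lost.

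The estimated gain of about 2% to 13% in interval width rests on equal SDs, a linear relation and a 40:40 split of the maximum 80 patients. Only the lower end uses a correlation from the documents. With 64 evaluable patients the proportional gain is nearly the same. SAP section 4 reports that the trial as a whole ended much smaller than planned, so absolute intervals may be wider than those shown and chance imbalance larger. The effect is on the width of descriptive intervals and their robustness to baseline imbalance. It does not bear on the primary or secondary conclusions.

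**What to change.** State in Protocol 10.1.8.3 that each EEG endpoint is analysed by ANCOVA with treatment, the baseline value of the same measure, and age. Baseline antipsychotic use, the randomisation stratum, may be added for consistency with 7.3.2, but the gain calculated here comes from the baseline value alone. If the unreadable part of the SAP already includes baseline, aligning the protocol wording is enough.

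The cost is one sentence and one degree of freedom per model. No new data are needed, and no patient is lost, because a change score already requires a baseline recording.

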10.2 OCULAR SAFETY SUB-STUDY

10.2.1 Flowchart

MAIN STUDY	Trial Periods	Screening Period	Randomised Treatment Period			Follow-up Period
	Visit	1	2	14	EOT	F/U
	Study Week	-4	0	24	52	56
Study Day	-28 to -7	1	169	365	393	
SUB-STUDY	Sub-study Visit	Screening	Pre*	6 months	12 months	
	Best Corrected Visual Acuity (BCVA)		X	X	X	
	Color Vision Test (F-M 100)		X	X	X	

* Ocular tests to be completed before first dose.

10.2.2 Background and Objective

In Phase I and II studies with BI 409306, the most frequently observed AEs were eye disorders. All of these AEs have been non-serious and mild to moderate in severity. These events have generally been reported as transient and resolve upon treatment discontinuation. While the frequency of these AEs generally increases with dose, at higher doses there is no obvious relationship between dose and maximum duration and intensity. Onset and duration of these events seem related to Cmax (i.e. in general, onset is approximately within the first 1-2 hours of administration and duration is approximately 30 to 120 minutes). However, first onset after dosing appears variable, with some subjects experiencing these events after first dosing and others only after subsequent dosing. There are no obvious differences in frequency of these events for elderly or CYP2C19 poor metabolizer subjects, but relevant data is limited [[c01694347-08](#)].

The objective of this sub-study is to further characterize the ocular safety of BI 409306 in a subset of patients from the main study.

10.2.3 Selection of Study Population

This sub-study will enroll approximately 50 patients from a subset of sites in the United States participating in the main study. Patients enrolled at the participating ocular sub-study sites will be required to complete all of the ocular safety assessments.

10.2.4 Sub-study Design

Best Corrected Visual Acuity and color vision will be evaluated at the baseline Visit 2 (pre-dose), 24 weeks and 52 weeks or EOT from a subset of the main study patient population.

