Early D/C Option 1: An EOT Visit must be conducted within 7 days of the last dose of study medication for patients who agree to conduct regularly scheduled visits after premature drug discontinuation. Thereafter, patients should be followed up according to the regular visit schedule for both in-clinic and phone visits. Visit 23 will be the final visit for patients choosing this Early D/C Option.
Early D/C Options 2-4: An EOT Visit must be conducted within 7 days of the last dose of study medication for patients who agree to conduct the remaining visits over the phone, or patients who agree to be contacted or data collected via alternative sources approximately one year after the patient was randomized.
- *** Patients who complete the treatment period will be scheduled for a Follow-Up Visit 28 days after Visit 23. Patients who prematurely discontinue study medication and choose Early D/C Option 1 will not need a Follow-Up Visit. Patients who prematurely discontinue study medication and choose Early D/C Options 2-4 will be scheduled for a Follow-Up Visit 28 days after the EOT visit. See Sections [3.3.4.1](#), [6.2.2](#), and [6.2.3](#).
- **** The End of Study CRFs will be completed at the time of the Follow-Up Visit for completed patients. Patients who prematurely discontinue study drug and remain in the study will have the End of Study CRFs completed one year after randomization.
- 1 Written informed consents/assents for main study and optional pharmacogenomics test for deoxyribonucleic acid (DNA) banking must be obtained before any study-related procedures and assessments are performed. The registration of patients for the study is through the Interactive Response Technology (IRT). Patients who sign the assent and reach the age of majority during the trial must sign the current version of the informed consent. Re-consenting may become necessary when new relevant information becomes available and should be conducted according to the sponsor's and IRB/IEC's instructions.
- 2 Female patients of childbearing potential must perform urine (dipstick) pregnancy test at in-clinic Visits 1 through Visit 23/EOT.
- 3 A 12-lead electrocardiogram (ECG) is to be performed during the scheduled visits or within 24 hours prior to the visit, except for Visit 1 (Screening Visit), where the ECG test will be performed only after a written informed consent/assent for main study has been obtained.

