BI 409306 was tested in a comprehensive panel of in vitro and in vivo General Pharmacology tests (non-GLP) and in the core battery of Safety Pharmacology tests (GLP). The major findings were cardiovascular effects which were similar to those described for other PDE inhibitors and considered to be secondary to a cGMP related vasodilatation. Repeat-dose oral toxicity studies were conducted with daily oral (gavage) administration of BI 409306 to mice, rats, and dogs for up to 13 weeks. Target organs identified in these studies were the cardiovascular system (rats and dogs), liver (rats), adrenal glands (rats), ovaries (rats), and spleen (rats). Adverse effects in rats were mainly limited to the highest dose tested. Only an adaptive finding in the adrenal glands of rats interpreted as being secondary to the cardiovascular effects occurred at lower dose levels. Cardiovascular effects in dogs occurred also at lower doses but can be monitored in clinical trials. Chronic toxicity studies in rats and dogs are ongoing. The genotoxicity profile of BI 409306 was tested in the standard battery of genotoxicity tests and a comet-assay in rats. The overall assessment revealed that BI 409306 is not genotoxic. BI 409306 was not teratogenic in rats and rabbits and, based on preliminary results, did not alter the fertility and early embryonic development in rats [[c01694347-08](#)].

Clinical Summary

In all 10 healthy volunteer trials, the most frequent drug related adverse events were visual side effects that occurred shortly after dosing, mostly resolved within 1 hour, i.e., in close connection to maximum BI 409306 plasma concentrations, as the concentration-time profile sharply and steeply peaks within the first 1-2 hours and then rapidly declines afterwards. Overall, there were no relevant changes observed for laboratory, electrocardiogram (ECG) recordings, and vital signs following treatment with BI 409306 when compared to placebo.

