10.2.5 Methods and Testing procedure

Testing conditions (i.e. exam room, chart distance, lighting conditions) should remain constant for each ocular testing visit. Patients who wear eye glasses or contact lenses should wear them for each of the visual acuity and color vision assessments.

Best Corrected Visual Acuity (BCVA)

BCVA will be determined using a Snellen chart at a 10 foot testing distance under standard lighting conditions.

Patients will be instructed to begin at the top of the Snellen chart and read down the chart until they reach a row where all letters on a line cannot be read correctly. The smallest line that a subject can read correctly at the 10 foot distance will be recorded.

BCVA will be determined and recorded at Visit 2 (pre-dose), 24 weeks and 52 weeks or EOT.

Farnsworth-Munsell 100 hue test (F-M 100)

Color vision testing using the Farnsworth-Munsell 100 hue test will be used to evaluate color vision or color vision deficiency. It consists of 93 colors mounted in plastic caps of incremental hue variations, housed in four separate cases. Two caps are fixed as pilot colors at either end of the panel in each case. Patients will be asked to place the color caps in order of hue between each of the fixed anchors. The final arrangement of the hue caps represents the aptitude of the visual system in discerning differences in color hue.

The standard software application included in the F-M 100 package will be used for scoring and analyzing the results. Total error score (TES) will be used as a measurement of color vision. Total error score and level of color vision deficiency classification (e.g. superior, average, low discrimination) will be recorded on the eCRF.

Examination of color vision will be performed at Visit 2 (pre-dose), 24 weeks and 52 weeks or EOT.

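### The ocular sub-study neither fixes nor records time since last dose and mixes on-drug with off-drug tests, so a finding of no change cannot rule out the short post-dose visual effect

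*Protocol*

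**What the plan says.** The ocular sub-study is in Protocol 10.2. It takes about 50 patients from a subset of US sites (10.2.3). It measures best corrected visual acuity (BCVA) on a Snellen chart and colour vision by the Farnsworth-Munsell 100 hue test (F-M 100, total error score).

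- **Schedule (10.2.4):** "Best Corrected Visual Acuity and color vision will be evaluated at the baseline Visit 2 (pre-dose), 24 weeks and 52 weeks or EOT". The footnote to the flowchart in 10.2.1 puts the baseline tests ahead of the first dose. There is no counterpart for the later tests.
- **Conditions held constant (10.2.5):** "Testing conditions (i.e. exam room, chart distance, lighting conditions) should remain constant for each ocular testing visit". Time since dose is not among them.
- **Known effect (10.2.2):** "Onset and duration of these events seem related to Cmax"; in general, "onset is approximately within the first 1-2 hours of administration and duration is approximately 30 to 120 minutes". The same paragraph says the events generally clear when treatment stops. Section 1.2 reports, for healthy volunteers, "visual side effects that occurred shortly after dosing, mostly resolved within 1 hour".
- **End of treatment:** under the main Flow Chart footnotes, completers have EOT at Visit 23. For early discontinuers, "An EOT Visit must be conducted within 7 days of the last dose of study medication"; Section 6.2.2 also accepts as soon as possible, so the gap can be longer.
- **Objective and analysis:** "The objective of this sub-study is to further characterize the ocular safety of BI 409306 in a subset of patients from the main study" (10.2.2). Section 10.2.8 plans descriptive change from baseline, including paired t-tests and confidence intervals.

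**The concern.** An effect that lasts between half an hour and two hours is visible only to a test that falls inside it. The ocular data could answer two questions: is there an objective change in acuity or colour vision shortly after a dose, and is there a change that persists over a year of treatment? Without time since dose, neither can be read cleanly. No change may mean no effect, or a test done after the effect had passed. A change may mean lasting impairment, or a test that happened to fall near peak.

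The last time point adds a second mixture. Patients who stopped drug days earlier are summarised together with patients still taking it, although the protocol itself expects these events to clear after stopping. At stake is what the clinical trial report can conclude about ocular safety from data already being collected.

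**Working it through.** The sub-study states no power or precision figure, so there is nothing to reproduce. The check is how often a test at an uncontrolled time would fall inside the effect.

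**Inputs from the Protocol**

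- Onset within about 1-2 h of a dose, duration 30-120 min (10.2.2).
- Twice-daily dosing about 12 h apart (4.1.4).
- Two post-baseline tests (10.2.4).
- About 50 patients (10.2.3), so about 25 on active drug if 1:1 allocation carries over to the sub-study sites.
- Dropout of 20% after one year (7.7).

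**Assumption:** the distribution of test time after dosing. The documents do not give it.

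**Step 1. Share of single tests inside the effect.** With test time spread evenly over T hours after a dose and an effect lasting d minutes, p = d / (60T). The chance that at least one of two independent tests falls inside is 1 - (1 - p)².

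| Duration d | p, T = 12 h | at least 1 of 2 | p, T = 8 h | at least 1 of 2 |
|---|---|---|---|---|
| 30 min | 30/720 = 4.2% | 8% | 30/480 = 6.3% | 12% |
| 60 min | 60/720 = 8.3% | 16% | 60/480 = 12.5% | 23% |
| 120 min | 120/720 = 16.7% | 31% | 120/480 = 25% | 44% |

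Among 25 active patients, that is between 25 × 0.042 = 1 and 25 × 0.25 = 6 Week 24 tests inside the effect, even if every patient had it.

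**Step 2. Variable onset and duration.** With onset uniform over 0-2 h and duration uniform over 0.5-2 h, simulation puts the share of single tests inside the effect at:

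- 10% for test times spread over 0-12 h
- 16% for 0-8 h
- 20% for 1-6 h
- 34% for 1-4 h
- 45% for 0.5-3 h

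If every test happened to fall exactly 2 h after the dose, the share would be 62%. The answer is therefore driven by visit habits.

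**Step 3. Off-drug tests.** The latest end of effect implied by 10.2.2 is 2 h onset + 2 h duration = 4 h after a dose. Seven days is 7 × 24 = 168 h. A test done days after the last dose covers none of the effect. If the 20% dropout of Section 7.7 applied to study drug in this subset, 0.20 × 25 = 5 active patients could have an off-drug EOT test pooled with about 20 on-drug Week 52 tests.

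**The case against.** The strongest reply is that the sub-study was not built to catch the acute effect. Its stated objective is general, and tests at baseline, 6 months and 12 months suit a check for lasting or cumulative change. The short effect is already described. A dedicated ocular study found no relevant changes (2.3), and earlier multiple-dose exposure was shorter: 14 days in Section 1.2 and 12 weeks in the schizophrenia trial listed in 9.2. Transient events also have their own route, because Section 5.3.6.2 requires verbatim recording of vision-related events and an ophthalmology assessment when severe. The smartphone platform in 4.3 confirms ingestion, so dose times may exist. The public text passes from 10.2.6 to 10.2.8, so 10.2.7 cannot be checked.

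Much of this stands. A reader might infer that the sub-study was added to measure the peak-related effect. The background describes only that effect, but the objective does not say so. Event reports narrow the gap to objective measurement of the acute effect.

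What remains is that nothing in the visible text of 10.2 links dose times to the ocular tests. Even if lasting change is the sole aim, a pre-dose baseline compared with follow-up tests at unknown times after dosing cannot separate lasting change from an acute one.

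**Conclusion.** The point holds as a limit on interpretation that is cheap to remove. As planned, a finding of no change in BCVA or total error score cannot be taken to exclude the transient effect, and a change cannot be assigned to acute or lasting causes. Both statements follow from the text and need no assumption about visit times.

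Three stronger readings are tempting, and the documents do not support them:

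- **That the tests mostly miss the effect.** With test times spread as assumed above, 4% to 45% fall inside it. Counting every minute up to 4 h as effect, with tests at 1-5 h, would give (4 - 1)/(5 - 1) = 75%. The documents do not say which pattern applies.
- **That testing up to 7 days after the last dose is general.** It concerns early discontinuers only; completers are tested at Visit 23.
- **That a specific loss of power follows.** That needs an F-M 100 effect size, which the documents do not give, and 10.2.8 plans a descriptive analysis with paired t-tests and makes no power claim.

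**What to change.** - **10.2.2:** state whether the target is transient or persistent change, and limit the conclusion to match.
- **10.2.5:** record the clock time of the last study-drug dose and of each ocular test. Keep the test at a consistent time relative to the patient's usual dose across follow-up visits, leaving dosing as it is.
- **10.2.8:** summarise change from baseline by time since last dose, and report EOT tests done after stopping study drug separately from on-drug tests.

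Moving the dose to the clinic to force a test near peak is not proposed. It would alter dosing and, against a pre-dose baseline, would confound lasting change with the acute effect.

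The cost is appendix wording, two eCRF time fields and some care in scheduling, with no new test. The downside is small subgroups among about 50 patients, so the split summaries will be imprecise and should stay descriptive.
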